- A list of active participants will be generated either through culling EMR data or talking with clinical teams that will serve as the primary list for their clinical teams to approach to describe the study and gauge interest.
- Services billed- no identifiers will be shared with the research team

Mental Health Provider Participants:

Select mental health providers will be invited to complete an online assessment with the research team. Staff participants will be invited to complete a confidential online survey. This includes exposure to the FOCUS app, if strategies or the program was incorporated into their treatment plans, and perceptions of how the program was adopted and implemented at their clinic.

Mental Health Provider Assessment:

Providers who receive FOCUS data

- Offered mHealth, i.e., the percent of each practitioner's eligible patients who are offered FOCUS
- Treatment Initiation, i.e., percent of consenting patients who followed their practitioner's guidance and went on to download FOCUS onto their smartphone and interact with the system at least once. Dashboard Use, i.e., the average number of times each practitioner logs on to the online FOCUS dashboard to view their individual patients' uploaded FOCUS data

The following will be captured via online confidential** survey (Qualtrics):

- The perception among practitioners that an innovation is agreeable, palatable, or satisfactory. (Measured via AIM / IAM / FIM).
- ORIC: Organizational Readiness for Implementing Change

Providers at the clinic who may not have been directly involved with the FOCUS Intervention (to provide contextual factors) through online confidential survey (Qualtrics):

- Organizational Readiness to Change Assessment (ORCA)
 - CMHC staff participants will complete 23 items using a 5-point bipolar rating scale (1-Strongly agree to 5-Strongly disagree). Constructs evaluated include clinical cooperation within the practice, clarity in patient care goals and process, level of support (e.g., training, budget, staffing) and typical receptivity to guidance (staff) and feedback (leadership).
- Absorptive capacity will be measured among CMHC practitioners who were engaged in IF or EF implementation at 0, 3, and 6 months using the 14-item ACAP Scale.
 - o The ACAP Scale evaluates dimensions of absorptive capacity including
 - Acquiring (e.g., searching for new information, motivation to use information)

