## UNIVERSITY of WASHINGTON

Analytic Approach. Our analyses seek to test the overall effect of our implementation strategies on implementation outcomes (Aim 1), mediators and moderators of those effects (Aim 2), and the impact of the strategies on patient outcomes (Aim 3). In Aim 1, the dependent variables of interest will be penetration and provider acceptability assessed at baseline (prior to initiation of the facilitation strategies), at 3 months (following the completion of the facilitation period), and at 6 months (following 3 months of having no exposure to facilitation). Given the nested data (i.e., time nested within clinicians and clinicians nested within agencies), analyses will rely on 3-level mixed effects regression models. Negative binomial regression with log offsets will be used to model rates, and linear regression will be used to model continuous outcomes. For all models, our independent variables of interest will be a binary indicator of internal versus external facilitation (measured at the organizational level), time, and their interaction. The magnitude and statistical significance of the interaction term will estimate the effect of the implementation strategy on change, or "growth," in outcomes over time. The impact of the intervention strategy on each outcome at each time will also be derived from these models. In addition, we will aggregate facilitylevel data and estimate the average weighted cost metrics across the sample of sites. Future commercial pricing of mHealth technology is unknown, so we will run scenarios that have different ranges of costs for FOCUS and explore the impact on the total program costs.

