In Aim 2, mediation will be tested using the product of coefficients approach for multilevel mediation analysis, building on the models in Aim 1. In this approach, the total effect of the implementation strategy is parsed into direct and indirect pathways associated with absorptive capacity, the mediator. Path "a" will represent the effect of the implementation strategy at the organizational level on the clinician-level assessment of absorptive capacity. Path "b" represents the relationship between this mediator and the clinician-level growth parameter, signifying change in outcomes over time. An unbiased estimate of the mediated effect is derived via the product of the "a" and "b" paths (i.e., a\*b) from these analyses. We will test the statistical significance of the mediated effects using the joint significance test and use Monte Carlo simulation methods to derive confidence intervals. Separate mediation models will assess whether absorptive capacity mediates the relationship between implementation strategy and, respectively, penetration, cost, and acceptability outcomes. Moderators of the implementation strategies' effects will be tested by adding terms for each hypothesized moderator and its interaction with the implementation strategy to the Aim 1 models. Specifically, these models will estimate the conditional relationships between the implementation strategies and implementation outcomes across different values of the putative moderators. Organization-level moderators (i.e., Readiness for Change, Organizational Culture, Urban or Rural designation) will be examined. The magnitude of the moderator effects will be probed using simple slopes analysis and region of significance analysis for multilevel models.

In Aim 3, we will use the same techniques as described in Aim 1 to develop 3-level linear mixed regression models that account for the nesting of time within patient and patient within organization to assess the impact of the implementation strategy on patient outcomes over time. We will use the methods described in Aim 2 to examine whether this relationship is moderated by organizational moderators and selected patient demographic characteristics (i.e., gender, race). We will also determine if patients' level of mHealth engagement mediates the relationship between implementation strategy and patient outcomes. All analyses will be conducted using MPlus to

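### Follow-up differences between facilitation arms are not adjusted for baseline scores the trial already collects; strategy-by-time removes baseline only as a change score

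*SAP*

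**What the plan says.** In the SAP's Analytic Approach, Aim 1, baseline belongs to the outcome: "the dependent variables of interest will be penetration and provider acceptability assessed at baseline (prior to initiation of the facilitation strategies", with months 3 and 6 as the other occasions. The model is given as: "our independent variables of interest will be a binary indicator of internal versus external facilitation (measured at the organizational level), time, and their interaction". The main test is strategy-by-time: "The magnitude and statistical significance of the interaction term will estimate the effect of the implementation strategy on change". A second set of results comes from the same fit: "The impact of the intervention strategy on each outcome at each time will also be derived from these models".

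Aim 3 carries this over to the patient scales: "we will use the same techniques as described in Aim 1 to develop 3-level linear mixed regression models".

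In Aim 2, path a is "the effect of the implementation strategy at the organizational level on the clinician-level assessment of absorptive capacity". Neither the visit nor the handling of baseline is stated. Protocol section 5.1 does provide a baseline value: "Absorptive capacity will be measured among CMHC practitioners who were engaged in IF or EF implementation at 0, 3, and 6 months".

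Neither document adds a baseline covariate or constrains the arms to equal baseline means.

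**The concern.** With strategy, time and their interaction in the model and baseline in the outcome vector, each arm has its own free baseline mean. The strategy effect at month 3 or 6 is then the difference in follow-up means (exactly so with categorical time and complete data). Any gap between the two sets of clinics at the start stays in the comparison to the extent that it persists.

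The interaction is a difference in change. It does remove the gap, but with a fixed coefficient of 1, which over-corrects when baseline and follow-up clinic means are less than perfectly correlated.

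With about ten clinics per arm, chance gaps are not small, and the SAP's Power Analysis says resources cap the number of clinics. Precision can therefore come only from better use of data in hand. A reader will also see two answers per outcome, the interaction and the visit difference, which may disagree because they treat baseline differently.

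**Working it through.** **Inputs.** From the SAP's Power Analysis: 20 clinics, 5 clinicians and 15 patients per clinic, between-organization ICC 0.19, between-patient ICC 0.45, between-provider ICC 0.30, two-sided alpha 0.05. Assumed: a 10:10 split (the protocol says arms are balanced but gives no ratio); total SD 1; 0.45 read as including the clinic share, so the patient share is 0.45 - 0.19 = 0.26; and the correlation of clinic effects between visits (CAC), which the documents do not give, set at 1.0, 0.7 and 0.5.

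**The SAP's own figure.** For a single visit, the design effect is 1 + 14 x 0.19 = 3.66, so the effective n per arm is 150/3.66 = 41. The detectable effect is (1.96 + 0.84) x sqrt(2/41) = 0.62, and power at d = 0.44 is about 51%. The stated 0.44 at 80% power is not reproduced for a single-visit contrast. The SAP does not say which contrast its figure refers to. That is a separate matter, and nothing below depends on it.

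**Size of a chance baseline gap (patient scales).** Clinic-mean variance v = 0.19 + 0.81/15 = 0.244. SE of the arm difference = sqrt(4 x 0.244/20) = 0.22 SD, half of 0.44. A gap of at least 0.22 arises in about 1 trial in 3, and of at least 0.44 in about 1 in 20. Balancing on clinic size and rural/urban setting (protocol 5.1) may reduce this by an unknown amount.

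**Three estimators, patient scales.** The covariance of clinic means between visits is c = CAC x 0.19 + 0.26/15.
- Visit contrast: v.
- Strategy-by-time: 2(v - c).
- Baseline-adjusted: v(1 - (c/v)^2) x (1 + 1/16). The last factor, with 16 = 20 - 4, is the cost of estimating the baseline slope from 20 clinics.
- Detectable effect at 80% power = (t.975 + t.80) x sqrt(4 x variance/20), with multiplier 2.963 on 18 df and 2.973 on 17 df (adjusted).

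| CAC | c | c/v | Visit | Interaction | Adjusted | Cut v visit | Cut v interaction | Detectable: visit / interaction / adjusted |
|---|---|---|---|---|---|---|---|---|
| 1.0 | 0.207 | 0.85 | 0.244 | 0.073 | 0.072 | 70% | 2% | 0.65 / 0.36 / 0.36 |
| 0.7 | 0.150 | 0.62 | 0.244 | 0.187 | 0.161 | 34% | 14% | 0.65 / 0.57 / 0.53 |
| 0.5 | 0.112 | 0.46 | 0.244 | 0.263 | 0.204 | 16% | 22% | 0.65 / 0.68 / 0.60 |

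The ratio c/v is also the share of a chance baseline gap expected to remain in the follow-up difference: 85%, 62% or 46%.

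**Other reading of the ICCs.** If 0.45 is additional to 0.19 and CAC is 1.0, then c = 0.19 + 0.45/15 = 0.220. Interaction = 0.048; adjusted = 0.0456 x 1.0625 = 0.0485. Adjustment is then about 1% worse than the interaction (detectable effect 0.29 for both).

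**Provider outcomes** (5 per clinic, 0.30 read as the total within-provider correlation, clinic ICC assumed, CAC 1.0):
- Clinic ICC 0.05: v = 0.05 + 0.95/5 = 0.24; c = 0.05 + 0.25/5 = 0.10; interaction 0.28; adjusted 0.198 x 1.0625 = 0.211. Cuts: 12% against the visit contrast, 25% against the interaction.
- Clinic ICC 0.10: v = 0.10 + 0.90/5 = 0.28; c = 0.10 + 0.20/5 = 0.14; interaction 0.28; adjusted 0.210 x 1.0625 = 0.223. Cuts: 20% against each.

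**The case against.** The strongest reply is that the main test already deals with baseline. Strategy-by-time is a difference in change, and with the SAP's ICCs and stable clinic effects it is as precise for patient scales as the adjusted estimate. That stands. A reader might infer that the interaction ignores baseline, or that adjustment can never lose. The documents support neither: the interaction removes baseline by subtraction, and at 20 clinics the cost of estimating the slope can cancel the gain.

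Further points:
- **Visit effects are secondary.** The SAP says they will also be derived, so the 70% applies to a secondary contrast. True, but they are promised results and would be reported.
- **Time may be linear.** The SAP does not say. With a straight line, complete data and CAC 1.0, the fitted month-6 difference weights the three visits -1/6, 1/3 and 5/6. Its variance is 0.207 + 0.0367 x 30/36 = 0.238 against 0.244, so little changes.
- **Penetration.** Offers, initiation and dashboard log-ins should be near zero before facilitation begins. The point does not extend to them.
- **Path a.** A reader might infer a planned unadjusted analysis. The SAP is silent, and its list covers predictors of interest, which need not be every covariate.
- **Selection.** If the arms differ systematically at baseline, for instance because patients join knowing their clinic's arm, a change contrast can be defended under parallel trends. This is a reason to keep the interaction as a supporting analysis.
- **Missing baselines.** Keeping baseline in the outcome vector lets the planned likelihood analysis retain people without a baseline score. This is a real, small cost of the change.

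**Conclusion.** The point holds in a limited form. The visit-specific effects for acceptability and the Aim 3 scales are not adjusted for baseline, and the interaction adjusts only by subtraction. The planned analysis is valid under randomisation. A reader might infer bias or an inflated type I error; nothing in the documents supports that. What is at issue is precision, and clarity about which contrast answers each aim.

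The case rests on three things: the visit-specific effects, where variance falls by about 16 to 70% for patient scales; provider outcomes, where it falls by about 12 to 25% across both contrasts; and any drift in clinic effects, where the gain over the interaction on patient scales reaches 14 to 22%. These figures depend on the assumed 10:10 split, CAC, reading of the ICCs and, for providers, clinic ICC. Without drift, the gain over the interaction on patient scales is about nil. The change is worth making because it is cheap and no clinics can be added.

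**What to change.** For provider acceptability and the Aim 3 patient scales, state in the SAP that the external-internal difference at month 3, and at month 6 where collected, comes from a mixed model of the follow-up waves with the individual's baseline score and the clinic-mean baseline as covariates. The qualifier matters because protocol 4.1 describes staff surveys only at 0 and roughly 3 months, whereas the SAP also lists month 6. Leave penetration as planned. Say whether time is categorical, and keep strategy-by-time as a supporting analysis.

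For path a, state the visit used. If follow-up absorptive capacity is the outcome, adjust it for its month-0 value in the same way.

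Cost: SAP wording, one or two clinic-level degrees of freedom, and a simple prespecified rule for a missing baseline score (for example, clinic-mean imputation), which the likelihood approach would not otherwise need. No new data are required.

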Aim 1. Evaluate and compare implementation outcomes. We will measure and compare FOCUS penetration among providers, acceptability within agencies, cost and cost effectiveness associated with FOCUS within CMHCs using EF or IF implementation approaches.

Aim 2. Examine moderators and mediators of implementation effects. We will examine the extent to which CMHC characteristics (i.e., readiness for change, organizational culture, urban vs. rural setting) moderate implementation outcomes. Consistent with the NIMH experimental therapeutics approach, we will evaluate mechanisms of action and examine whether absorptive capacity (practitioner—level target) mediates the effect of EF and IF on implementation outcomes.

Aim 3. Evaluate and compare patient outcomes. We will measure and compare whether the

implementation strategies differentially affect FOCUS patients' psychiatric symptom severity, recovery, and illness management capacity. We will also examine whether mHealth engagement (patient-level target) mediates the effects of EF and IF on patient outcomes.

1.6 Study design. Provide a one-sentence description of the general study design and/or type of methodology.

Your answer will help HSD in assigning applications to reviewers and in managing workload. Examples: a longitudinal observational study; a double-blind, placebo-controlled randomized study; ethnographic interviews; web scraping from a convenience sample of blogs; medical record review; coordinating center for a multi-site study.

multi-site site hybrid type III effectiveness/implementation study

1.7 Intent. Check all the descriptors that apply to your activity. You must place an "X" in at least one box.

This question is essential for ensuring that your application is correctly reviewed. Please read each option carefully.

Desci	riptor
1.	. Class project or other activity whose purpose is to provide an educational experience for the researcher (for example, to learn about the process or methods of doing research).
2.	Part of an institution, organization, or program's own internal operational monitoring.
3.	s. Improve the quality of service provided by a specific institution, organization, or program.

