
return on investment considerations that would make the addition of an internal facilitator more appealing and contextually appropriate. There may be benefits in using recognized members of the clinical setting who can capitalize on existing relationships and awareness of workflows and practice processes, have legitimacy and trust, have access to patient records, engage in clinical team meetings, and conduct facilitation activities with CMHC staff in person, thus enhancing penetration. We propose to use IF and EF to engage providers and compare the effects of both models on patient and implementation outcomes. Key implementation variables. A host of implementation research outcomes have been articulated for studies focused on improving the quality of health services. 46 The promise of mHealth rests largely in its ability to efficiently transform contemporary healthcare at a large scale. 47, 48 Therefore, examining the impact of the implementation strategy on penetration of a practice within a service setting, acceptability (perception that an innovation is agreeable, palatable, or satisfactory), cost-effectiveness (value for money of alternative approaches) and affordability (i.e., the expense of the particular intervention) are particularly critical. Organizational factors are critical to effective implementation: With growing recognition that "bad systems trump good programs," 49 the role of organizational influences on implementation has become widely recognized. 50-52 Critical factors influencing implementation success include the extent to which an organization is ready to engage in a change effort. 53 Organizational readiness for change varies depending on how much members of an organization determine task demands, resource availability, and situational factors to be favorable. A strong organizational culture (i.e., shared assumptions, values, and beliefs that govern how people behave in an organization) has repeatedly been found to predict positive implementation and service quality outcomes.52, 54, 55 We will directly examine whether our implementation strategies have a differential impact on implementation outcomes depending on an organization's culture and readiness for change.

b. Experience and preliminary work. Briefly describe experience or preliminary work or data (if any) that you or your team have that supports the feasibility and/or safety of this study.

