 - Assimilating (e.g., communication of new ideas and concepts across stakeholders, cross departmental sharing of information)
 - Transforming (e.g. ability to structure and use collected information, linking existing knowledge with new insights, applying new knowledge to practical work), and
 - Exploiting new knowledge in practice (e.g., adapting practices according to new knowledge, working more effectively by adopting new technologies)
 - IF/EF self-report: Clinicians will report the number of access points to the clinician dashboard, distribution of weekly reports to the clinical team, and correspondence of data derived from the dashboard to treatment targets.
 - **IP addresses are collected by Qualtrics which may or may not be potentially identifiable, but will not be used by the research team as data.

Key informant interviews related to costing procedures will also be completed at a select number of study locations. Interviews will be conducted remotely by a trained research team member. Questions will be related to time, effort, and resources dedicated to the study. Interviews will last approximately 60 minutes, and be audio-recorded and later transcribed.

(5.2) Data sources. For all types of data that you will access or collect for this research: Identify whether you are obtaining the data from the subjects (or subjects' specimens) or whether you are obtaining the data from some other source (and identify the source).

If you have already provided this information in Question 5.1, you do not need to repeat the information here.

- 1) Self-report and interview-based measures obtained directly from CMHC staff participants by trained evaluators about services billed for and time allocation (for costing only).
- 2) mHealth engagement data recorded by the FOCUS system and uploaded to a secure server.

- 3) Self report symptom and self-management ratings obtained via Qualtrics survey.
- 4) Confidential staff questionnaire responses via Qualtrics.
 - **IP addresses are collected by Qualtrics which may or may not be potentially identifiable, but will not be used by the research team as data.
- **5.3 Retrospective/prospective.** For all types of data and specimens that you will access or collect for this research: Describe which data are:
 - Retrospecitve (i.e., exist at the time this application is sent to HSD)
 - Prospective (do not yet exist)
 - Both retrospective and prospective (for example, past and future school records)

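### Aim 1 promises an EF-versus-IF comparison of cost and cost effectiveness, but the SAP specifies no between-arm cost estimate and no cost-effectiveness analysis

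*SAP*

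**What the plan says.** Protocol 1.5, Aim 1, lists among the outcomes to be measured and compared "cost and cost effectiveness associated with FOCUS within CMHCs using EF or IF implementation approaches". Protocol 1.8 (Background) counts "cost-effectiveness (value for money of alternative approaches) and affordability" among the outcomes it regards as especially important, so it understands cost effectiveness as a comparison between alternatives.

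In the SAP, Analytic Approach, the Aim 1 models are defined first: "the dependent variables of interest will be penetration and provider acceptability assessed at baseline" and at two later times. The arm term belongs to those models: "For all models, our independent variables of interest will be a binary indicator of internal versus external facilitation", with time and the interaction of the two. Cost is then added separately. The team will combine the data by facility and "estimate the average weighted cost metrics across the sample of sites". Because the future price of the app is unknown, "we will run scenarios that have different ranges of costs for FOCUS and explore the impact on the total program costs".

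The SAP's Aim 2 text names cost once more, as one of three outcomes for which absorptive capacity is to be tested as a mediator of the strategy effect.

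On cost inputs, Protocol 5.1 says the key-informant costing interviews will be "completed at a select number of study locations". Other sources are also described: billed services from the medical record (5.1), administration and finance staff supplying de-identified data (2.2), and staff reports of billed services and time use (5.2). Protocol 4.1 says staff participants are chosen purposively, and mentions both arms.

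**The concern.** Protocol 1.8 sets the possibility that a few external facilitators could serve many sites cheaply against return-on-investment arguments for an internal one. It also says that the earlier IF pilot had no comparator arm and could not separate out facilitator costs. Whether IF is worth its resources is therefore a main reason for running this trial.

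That question needs cost by arm, a difference with its uncertainty, and a link from cost to effect. The SAP states none of these. If they stay unstated, the contrast, the weights and the effectiveness measure will be chosen after the data are seen, or the comparison will not be made.

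**Working it through.** The documents give no sample size, power or precision for cost, so there is no figure of the plan's own to reproduce. The check is mainly a comparison of texts.

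**Step 1. What SAP Aim 1 specifies for each outcome that Protocol Aim 1 promises**

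| Element | Penetration, acceptability | Cost | Cost effectiveness |
|---|---|---|---|
| Estimator | 3-level mixed regression | Weighted mean over sites | None |
| Arm term | Yes | Not stated | None |
| Between-arm difference | Interaction, and at each time | Not stated | None |
| Uncertainty | Significance of the interaction | Not stated | None |
| Weights | Not applicable | Mentioned, not given | None |
| Effect denominator | Not applicable | Not applicable | None |
| Power or precision | d = 0.55 for provider outcomes | None | None |

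The price scenarios act on total programme cost and are not said to be run by arm.

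**Step 2. Does the Aim 2 cost mediation supply the contrast?**

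- It extends the Aim 1 models, and no Aim 1 model has cost as its outcome.
- Its second path runs to a clinician-level rate of change, whereas Aim 1 aggregates cost by facility. No repeated clinician-level cost measure is described.
- Its joint significance test and Monte Carlo intervals concern the product of the two paths, not the IF minus EF cost difference.
- It does not deal with cost effectiveness.

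**Step 3. Precision of a by-arm contrast (illustration)**

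Inputs: 20 clinics (SAP, Power Analysis); two-sided alpha 0.05 (same place); equal arms, an assumption because neither document gives clinics per arm. The calculation uses unweighted means and equal variances. With n clinics per arm, in units of the between-clinic SD of cost:

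Half-width = t(0.975, 2n − 2) × √(2/n)

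- n = 10 (all clinics costed): 2.101 × 0.447 = 0.94 SD
- n = 5 (assumed): 2.306 × 0.632 = 1.46 SD
- n = 3 (assumed): 2.776 × 0.816 = 2.27 SD

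At 10:10 and 80% power, the detectable difference is (1.960 + 0.842) × √(2/10) = 1.25 SD by the normal approximation, and 1.32 SD by the noncentral t with 18 degrees of freedom.

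The cases n = 5 and n = 3 appear in neither document. They show only how precision falls as fewer clinics are costed.

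**The case against.** The strongest reply is that the SAP does foresee a strategy effect on cost, because the Aim 2 mediation model treats strategy as exposure and cost as outcome. This stands as far as it goes: it would be wrong to say that the SAP never links arm to cost. As Step 2 shows, though, it does not yield the Aim 1 comparison. It presupposes an Aim 1 cost model that has not been written.

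Three stronger readings are tempting, and the documents do not support them.

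- A reader might infer that the SAP commits to one figure with the arms combined, which under equal weights would be the same whichever arm cost more. That is the natural sense of an average over the sample of sites, but the sentence is silent on arm and does not rule out averaging within arm. The data are still to be collected, so the comparison is unspecified, not impossible.
- A reader might infer that all cost data come from a few sites picked for convenience. Only the key-informant interviews are limited to some sites. Other cost sources are described, and the documents do not say how the interview sites are chosen.
- A reader might infer that a split by arm would lose the protection of randomisation. That is a risk for interview-based inputs if the selected sites are unbalanced between arms. It does not follow from the text.

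The half-widths describe how precise a contrast could be. They do not measure the omission, and they say nothing about which clinics should be costed.

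**Conclusion.** The point holds as a gap between the promised comparison and the stated analysis. SAP Aim 1 specifies no EF-versus-IF cost contrast. Cost effectiveness is analysed nowhere in either document, so that part of Aim 1 goes unanswered on any reading. The Aim 2 cost mediation has no Aim 1 cost model to build on.

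The consequence in money cannot be sized, because the documents give no costs and no between-clinic SD. What can be said is that a contrast using all 20 clinics would be imprecise: a half-width of about 0.94 between-clinic SDs, assuming a 10:10 split, unweighted means and equal variances. The number of clinics costed therefore matters and should be fixed in advance. This should be corrected before the cost data are analysed.

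**What to change.** Replace the SAP's cost sentence with the following.

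1. Mean cost per clinic and per patient **by arm**, with the weights and the costing perspective stated.
2. The IF minus EF difference with a 95% interval at clinic level, suited to about 20 clusters. A t-based interval is a reasonable main choice, with an arm-stratified bootstrap of clinics as a check, because a bootstrap with ten or fewer clinics per arm tends to give intervals that are too narrow.
3. Incremental cost against **one pre-named** penetration measure from Protocol 5.1 (patients offered FOCUS, treatment initiation or dashboard use). Resample cost and effect together by clinic within arm. Show net benefit beside the ratio, because the ratio is unstable when the penetration difference is near zero.
4. The app-price scenarios run within each arm.
5. An explicit cost model for the Aim 2 mediation to build on, at a level that matches how cost is measured.
6. The number of clinics supplying each kind of cost input. If interview-based inputs come from only some clinics, draw those at random within arm and urban/rural stratum.

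This costs SAP text, modest extra analysis and a random draw of interview sites if not all are used. Most of it uses data already planned. The downside is that the wide intervals will be visible.
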